Part D may be initiated while Parts A, B, and C are ongoing after review of safety, tolerability, and PK data. After all Part D1 subjects complete the Day 15 Visit, a blinded review of all available safety and PK data will be conducted by the Vertex study team and lead investigator(s). Dosing in Parts D2, E, and F will start after this review, if supported by safety and PK data.

VX-445 will be dosed qd.

Part D1 has 1 VX-445 dose level (mid: 100 mg qd). Part D2 has 3 VX-445 dose levels (low: 50 mg qd; mid: 100 mg qd; high: 200 mg qd). The TC-high dose of VX-445 in Part D2 does not exceed the highest dose that was safe and well tolerated in healthy subjects dosed with TC in Part C. Parts E and F will use the highest dose used in Part D2 (200 mg qd).

Randomization will be stratified by ppFEV₁ in Parts D2, E, and F. Randomization will not be stratified in Part D1 because of the small number of subjects in that Part

(N ~ 8).

Schematics of the Part D, E, and F treatment periods are shown below. Each part also includes a 4-week screening period and a 4-week safety follow-up period.

Part D1: Subjects with F/MF genotypes

	Period 1 (4 weeks)	Period 2 (1 week)	
Screening Period (4 weeks)	TC-mid (VX-445/TEZ/IVA) N = 6	TEZ/IVA	Safety Follow-up Period (4 weeks)
	Triple Placebo N = 2	Dual Placebo	

Dosing Period 2 is included in Parts D1 and D2 to enable a more thorough evaluation of VX-445 exposure-response relationships by conducting PK and PD assessments during the VX-445 washout.

Part D2: Subjects with F/MF genotypes

	Period 1 (4 weeks)	Period 2 (1 week)	
Screening Period (4 weeks)	TC-high (VX-445/TEZ/IVA) N = 18	TEZ/IVA	Safety Follow-up Period (4 weeks)
	TC-mid (VX-445/TEZ/IVA) N = 12		
	TC-low (VX-445/TEZ/IVA) N = 9		
	Triple Placebo N = 9	Dual Placebo	

In Parts D1 and D2, placebo is the control because efficacy has not been established for a corrector, potentiator, or any corrector/potentiator combination in subjects with F/MF genotypes.

Part E: Subjects with F/F genotype

	Run-in Period (4 weeks)	Period 1 (4 weeks)	Washout Period (4 weeks)	
Screening Period (4 weeks)	TEZ/IVA	TC-high (VX-445/TEZ/IVA) N = 18	TEZ/IVA	Safety Follow-up Period (4 weeks)
		Placebo + TEZ/IVA N = 6		

The Washout Period is designed to evaluate the effect on PD and efficacy endpoints as subjects step down from TC to TEZ/IVA.

TEZ/IVA is the control because results from a previous study (Study VX11-661-101)

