	Days -28 to -1	Day 1 ^c	Day 8 for Part D1 only (± 1 day)	Day 15 (± 2 days)	Day 29 (± 2 days)	Period 2 Visit ^d		
Informed consent	X							
Randomization ^e		X						
Demographics	X							
Medical history	X							
CFQ-R ^{f,g}		X		X	X			
Weight ^h	X	X	X	X	X		X	
Height ^h	X							
Vital signs ⁱ	X	X	X	X	X	X	X	
Pulse oximetry ⁱ	X	X	X	X	X	X	X	

^a All assessments will be performed before dosing, unless noted otherwise. Assessments that are collected before and after dosing will only be collected once if study drug is not administered on the day of the visit (i.e., if subject prematurely discontinued study drug treatment).

^b If the subject prematurely discontinues study drug treatment, an ETT Visit should be scheduled as soon as possible after the decision to terminate study drug treatment. Subjects who prematurely discontinue treatment will be required to complete the Safety Follow-up Visit. If the ETT Visit occurs 3 or more weeks after the last dose of study drug, the ETT Visit will replace the Safety Follow-up Visit, and a separate Safety Follow-up Visit will not be required.

^c To be eligible to continue into the Treatment Period, subjects must have stable CF disease and have remained on stable CF medication regimen during the 28 days before the Day 1 Visit AND must not have had an acute non-CF illness within 14 days before the Day 1 Visit. See [Section 9.1.2.4](#).

^d The Period 2 Visit will occur 6 to 10 days after the actual date of the Day 29 Visit.

^e Randomization may occur on the previous day (Day -1 Visit) after all inclusion and exclusion criteria have been confirmed.

^f CFQ-R must be completed before the start of any other assessments scheduled at that visit.

^g The predose assessment on the Day 1 Visit may be performed on the previous day (Day -1 Visit) if randomization has occurred.

^h Weight and height will be measured with shoes off.

ⁱ Vital signs and pulse oximetry will be collected after the subject has been seated for at least 5 minutes.

Table 3-6 Study VX16-445-001: Schedule of Assessments for Parts D1 and D2

Event/Assessment ^a	Screening	Treatment Period					ETT Visit ^b	Safety Follow-up 28 (± 7) Days After Last Dose
		Period 1			Period 2			
	Days -28 to -1	Day 1 ^c	Day 8 for Part D1 only (± 1 day)	Day 15 (± 2 days)	Day 29 (± 2 days)	Period 2 Visit ^d		
Physical examination ^j	Complete	Abbrev.		Abbrev.	Abbrev.		Abbrev.	Complete
Standard 12-lead ECG ^k	X	X	X	X	X		X	X
Sweat chloride ^{g,l}	X	X	X	X	X	X ^m	X	X

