8 STATISTICAL ANALYSIS

8.1 General Considerations

The analysis will be performed for each part, and presented by treatment group and overall, for the Treatment Period, unless specified otherwise. The treatment groups are defined as follows:

- Part D: F508del/MF genotypes group
 - Placebo, TC-low, TC-mid, and TC-high. The pooled TC-mid groups and the pooled placebo groups from Parts D1 and D2 will be used in all efficacy, pharmacodynamic (PD) and safety analyses for Part D.
- Part E: F508del/F508del genotype group
 - TEZ/IVA and TC-high.
- Part F: F508del/MF genotypes group
 - Placebo and TC2-high.

The Schedule of Assessments is provided in [Appendix A](#). The precision standards for reporting safety and efficacy variables are provided in an internal Biometrics document that specifies the programming rules including the precision for derived variables.

All individual subject data for those randomized or dosed with any amount of study drug will be presented in data listings.

Continuous variables will be summarized using the following descriptive summary statistics: the number of subjects (n), mean, SD, standard error (SE), median, minimum value (min), and maximum value (max). SE may not be reported for safety summary tables.

Categorical variables will be summarized using counts and percentages. Percentages will be presented to 1 decimal place.

Baseline value, unless otherwise specified, will be defined as the most recent non-missing measurement (scheduled or unscheduled) collected before the first dose of study drug on Day 1 of the Treatment Period. For ECG, baseline will be defined as the most recent non-missing measurement (or the average of triplicate measurements, if the most recent non-missing

measurement is obtained in triplicate), before the first dose of study drug on Day 1 of the Treatment Period.

Absolute change from baseline will be calculated as postbaseline value – baseline value.

Relative change from baseline will be calculated as (postbaseline value – baseline value)/baseline value.

Treatment-emergent (TE) period for Parts D and F will include the time from the first dose of study drug in the Treatment Period until 28 days after the last dose of study drug or end of study date (based on end of follow-up visit in CRFs), whichever occurs first.

For Part E, the TE period will be defined separately for the Run-In Period, and the Treatment Period:

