- The TE period for the Run-in Period will include the time from the first dose of study drug in the Run-in Period to: (1) the first dose of study drug in the Treatment Period for subjects who complete the Run-in Period and continue to the Treatment Period, or (2) 28 days after the last dose of study drug in the Run-in Period or end of study date (based on end of follow-up visit in CRFs), whichever occurs first, for subjects who do not continue to the Treatment Period (e.g., subjects who do not meet the criteria to enter the Treatment Period and re-enter Study 661-110).
- The TE period for the Treatment Period will include the first dose of study drug in Period 1 of the Treatment Period to 28 days after the last dose of study drug or end of study date (based on end of follow-up visit in CRFs), whichever occurs first.

Unscheduled visits: Unscheduled visit measurements will be included in analysis as follows:

- In scheduled visit windows per specified visit windowing rules
- In the derivation of baseline and last on-treatment measurements
- In the derivation of maximum and minimum on-treatment values, and maximum and minimum change from baseline values for safety analyses
- In individual subject data listings as appropriate

Visit windowing rules: The analysis visit windows for protocol-defined visits are provided in [Appendix B](#).

Spirometry (ppFEV1) will be used for both efficacy and safety purposes. For efficacy analysis, the assessments will follow the visit windowing rules for efficacy. For safety analysis, the assessments at both pre-dose and 5 hours postdose on nominal days 1 and 15 will be used.

Incomplete/missing data will not be imputed, unless specified otherwise.

Outliers: No formal statistical analyses will be performed to detect or remedy the presence of statistical outliers, unless specified otherwise.

Multiplicity: There will be no multiplicity adjustment for performing multiple hypothesis tests, unless specified otherwise.

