The adjusted means and 95% confidence intervals (CI) of the average treatment effect through Day 29 (Day 15 and Day 29 only) for each triple combination, with a 2-sided *p*-value will be estimated within MMRM using PROC MIXED in SAS, for all within-treatment and between-treatment comparisons, for each part, separately. Contrasts based on the fixed effects in the model, defined at the baseline covariate mean for the combined treatment groups using unique subjects in the FAS who have at least one post-baseline measurement through Day 29, will be used to estimate the average treatment effect across post-baseline visits through Day 29. Day 8 data will not be included in the model for the through Day 29 analysis for Part D.

Further, the adjusted mean and 95% CI of the treatment difference between each triple combination and placebo or TEZ/IVA at each post-baseline visit through Day 29 will be provided along with the corresponding *p*-value, for each part. In addition, the adjusted mean and 95% CI of the within-treatment difference at each post-baseline visit through Day 29 for each treatment group will be provided along with the *p*-value, for each part.

The adjusted mean (with 95% CI) obtained from the MMRM analysis at each post-baseline visit through Day 29 will be plotted by treatment group, for each part. In addition, a waterfall plot showing the subject-level absolute change in ppFEV₁ at Day 29 will be presented, by treatment group.

In addition, for each part, descriptive analyses of the change from baseline will be performed using pre-dose records for all treatment groups by post-baseline visit through the safety follow-up visit.

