8.4.2 Clinical Laboratory

For the treatment-emergent laboratory assessments, the observed values and change from baseline values of the continuous hematology, chemistry, and coagulation results will be summarized in SI units at each scheduled visit, by treatment group and part.

The number and percentage of subjects meeting at least 1 threshold analysis criterion event, during the TE period for Parts D and F, or the TE period for Treatment Period for Part E, will be summarized by treatment group and overall for each part. The threshold analysis criterion shift from baseline will also be summarized for selected laboratory parameters. The threshold analysis criteria are provided in [Appendix H](#).

For select LFT laboratory test (alanine aminotransferase [ALT], aspartate aminotransferase [AST], alkaline phosphatase [ALP], and total bilirubin), a scatter plot of the maximum treatment-emergent value versus the baseline value corresponding to xULN will be presented. Further, a scatter plot of the maximum treatment-emergent value of ALT and AST, separately, versus the maximum treatment-emergent value of total bilirubin corresponding to xULN will also be presented by treatment group, for each part.

Results of abnormal urinalysis and positive urine/serum pregnancy test will be listed in individual subject data listings only.

In addition, a listing containing individual subject hematology, chemistry, and coagulation values outside the normal reference ranges will be provided. This listing will include data from both scheduled and unscheduled visits.

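### In Part D, pooling D1 gives TC-mid and placebo an extra Day 8 safety look that TC-low and TC-high lack, so the ever-crossed and extreme-value safety outputs compare doses on slightly unequal schedules

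*SAP*

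**What the plan says.** The Part D schedule (Protocol Table 3-6, repeated as SAP Table 11-1) has a column headed "Day 8 for Part D1 only (± 1 day". At that visit D1 subjects have chemistry and hematology, urinalysis, ECG, vital signs, weight, pulse oximetry, spirometry and sweat chloride, but no coagulation sample. SAP Appendix B accordingly defines a Day 8 safety visit in Part D for D1 only.

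D1 has two arms, "TC-mid (VX-445/TEZ/IVA) N = 6" and "Triple Placebo N = 2". D2 has four, the largest being "TC-high (VX-445/TEZ/IVA) N = 18". SAP 8.1 then says "The pooled TC-mid groups and the pooled placebo groups from Parts D1 and D2 will be used in all efficacy, pharmacodynamic (PD) and safety analyses".

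The laboratory table in SAP 8.4.2 reports "The number and percentage of subjects meeting at least 1 threshold analysis criterion event, during the TE period for Parts D and F". SAP 8.4.3 and 8.4.4 use the same kind of count for ECG and vital signs. SAP 8.4.2 also plans threshold shifts and plots of the maximum treatment-emergent ALT, AST, alkaline phosphatase and total bilirubin, and 8.4.5 a shift to the lowest oxygen saturation. Unscheduled values also enter, under SAP 8.1: "In the derivation of maximum and minimum on-treatment values, and maximum and minimum change from baseline values for safety analyses".

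For ppFEV1, SAP 8.3.1.1.1 says "Day 8 data will not be included in the model for the through Day 29 analysis for Part D". No corresponding sentence exists for the safety outputs, and none of them is planned by D1 versus D2.

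**The concern.** A count of subjects who ever cross a threshold, or a subject's maximum or minimum, tends to rise with the number of measurements. If one dose group is measured more often than another, part of any difference between them reflects the schedule and not the drug.

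The extra look is not ordered by dose. It favors detection in TC-mid over both TC-low and TC-high, which can blur a dose trend. It also favors detection in placebo over TC-low and TC-high, which makes those two doses look slightly better against placebo. Safety and tolerability is a primary objective of Part D, and these tables will be read across placebo, low, mid and high dose in groups of 9 to 18, where a difference of a single subject can draw comment.

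**Working it through.** **Arm sizes.** D1: TC-mid 6, placebo 2. D2: TC-high 18, TC-mid 12, TC-low 9, placebo 9. The sum 6 + 2 + 18 + 12 + 9 + 9 = 56 reproduces the Part D total in Protocol 12.1.2.2 and SAP 6.2.1.2.

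**Share with a scheduled Day 8 look.** TC-mid 6/18 = 33.3%; placebo 2/11 = 18.2%; TC-low 0/9; TC-high 0/18.

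**Scheduled chemistry/hematology draws after baseline, from Appendix B.** Before follow-up, D1 has Days 8, 15 and 29 and D2 has Days 15 and 29.
- TC-mid: (6×3 + 12×2)/18 = 2.33
- Placebo: (2×3 + 9×2)/11 = 2.18
- TC-low and TC-high: 2.00

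The SAP ends the treatment-emergent (TE) period no later than 28 days after the last dose, and Safety Follow-up is at 28 ± 7 days, so that draw may or may not count. If it does, the means are 3.33, 3.18 and 3.00.

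**Expected share ever crossing when the true risk is equal.** The documents give no crossing rate. Assume a chance p per draw, the same in every arm and independent between draws. With k draws, P(at least one crossing) = 1 − (1 − p)^k, averaged over the D1 and D2 subjects in each arm. At p = 5% without follow-up:
- D1 subject: 1 − 0.95³ = 14.26%
- D2 subject: 1 − 0.95² = 9.75%
- TC-mid: (6×14.26 + 12×9.75)/18 = 11.25%
- Placebo: (2×14.26 + 9×9.75)/11 = 10.57%
- TC-low and TC-high: 9.75%

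| p per draw | Without follow-up: mid / placebo / low and high | With follow-up: mid / placebo / low and high |
|---|---|---|
| 1% | 2.32 / 2.17 / 1.99% | 3.29 / 3.15 / 2.97% |
| 5% | 11.25 / 10.57 / 9.75% | 15.69 / 15.04 / 14.26% |
| 10% | 21.70 / 20.47 / 19.00% | 29.53 / 28.43 / 27.10% |
| 20% | 40.27 / 38.33 / 36.00% | 52.21 / 50.66 / 48.80% |

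**In subjects.** Without follow-up, the expected excess in TC-mid is 6p(1 − p)². This is 0.06 at p = 1%, 0.27 at 5%, 0.49 at 10% and 0.77 at 20%. For placebo it is 2p(1 − p)², or 0.09 at 5%. It stays below one subject throughout.

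**ECG.** D2 has five scheduled looks (Day 1 postdose, Day 15 predose and postdose, Day 29, follow-up) and D1 has six. The means are 5.33 in TC-mid and 5.00 in TC-high; at p = 5% the shares are 23.91% and 22.62%.

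**Transient abnormalities.** Assume onset uniform over Days 1 to 29.
- A 7-day episode is caught by D1 draws if onset falls in 21 of the 28 days (75%) and by D2 draws in 14 of 28 (50%). Pooled TC-mid detects (6×75 + 12×50)/18 = 58%, and TC-high 50%.
- A 14-day episode is caught in every case on both schedules, so the gap is zero.
- An abnormality visible only around Day 8, present in a share q of subjects, is found by scheduled testing in q/3 of TC-mid, 2q/11 of placebo and none of TC-low or TC-high. At q = 20% these are 6.7%, 3.6% and 0%.

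**The case against.** The strongest reply is that the artefact is smaller than chance variation. One subject is 1/18 = 5.6% of TC-mid and 1/9 = 11.1% of TC-low, while the expected excess at p = 5% is about 0.3 of a subject. Within-subject correlation would shrink it further. Safety is descriptive, so no test or decision rule is touched. Counting all values in the TE period is also what Protocol 12.3.5.2.2, 12.3.5.3.2 and 12.3.5.4.2 call for. Much of the information is already visible: Day 8 has its own analysis visit, and out-of-range chemistry and hematology values are listed. All of this stands. It limits the importance of the point and rules out restricting the main tables. It does not make the schedules equal in the ever-crossed and extreme-value outputs.

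The documents do not support several stronger readings that a reader might infer:
- *That every Day 8 assessment distorts a safety table.* Safety spirometry uses nominal Days 1 and 15 only, urinalysis is only listed, and coagulation is not sampled at Day 8.
- *That adverse event counts are inflated in the same direction.* Clinically significant test findings become AEs, so a link is possible. But AEs are collected continuously, and nothing in the documents allows the effect to be sized.
- *That the SAP recognized this imbalance for efficacy and overlooked it for safety.* It drops Day 8 from the ppFEV1 model without giving a reason.
- *That the bias is large because the ratio is 11.25/9.75 = 1.15.* The absolute gap is 1.5 points, and with follow-up counted the ratio is 15.69/14.26 = 1.10.

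**Conclusion.** The concern holds in limited form. The Part D threshold counts for laboratory tests other than coagulation, ECG and vital signs (including weight), the threshold shifts, the maximum liver-test plots and the lowest-oxygen-saturation shift compare dose groups on unequal numbers of scheduled looks. The excess is in TC-mid first and placebo second.

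On average it is worth a fraction of one subject per arm. That size rests on an assumed per-draw crossing rate, equal true risk and independence between draws. Correlation makes it smaller; an early transient effect makes it larger, and a finding confined to the days around Day 8 could be picked up by scheduled testing only in TC-mid and placebo. Unscheduled values could move the gap either way. The reason to act is that a cross-dose reading of a primary objective can be put on a common schedule at little cost.

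**What to change.** Keep the pooled TE-period tables as planned, with all scheduled and unscheduled values. In SAP 8.4.2 to 8.4.5 add, for Part D only, a companion version of the affected threshold, shift and extreme-value outputs, in one of two forms:
- all subjects, leaving out scheduled D1 Day 8 values and the retests they triggered; or
- D2 subjects only (placebo 9, TC-low 9, TC-mid 12, TC-high 18).

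State that the companion version is the one for reading across doses. In the pooled tables, footnote the subjects whose only qualifying value was at Day 8, so that no event is hidden. No flag on AEs is needed: the AE fields listed in Protocol 13.1.1.3 do not link an event to a test.

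Either form brings the gap in scheduled looks to zero. At the assumed p = 5%, all four arms would then have an expected 9.75% without follow-up or 14.26% with it. The cost is a few lines of SAP text and a few extra tables. The first form also needs a written rule for identifying retests triggered by Day 8; the second avoids that rule but leaves out the 8 D1 subjects.

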 Part E: *F508del*/*F508del* (F/F) genotype

Investigational Drug **Active substance: VX-445 (Parts A, B, C, D, E, and F)**
 Activity: CFTR Corrector (increased Cl⁻ secretion)
 Strength and route of administration:
Tablet: 20-mg, 50-mg, and 100-mg tablets for oral administration
IV dose: 0.1 mg/mL for IV administration (Cohort A7 only)
Oral dose:
 Parts A, B, and C: Doses starting at 20 mg. No dose will be predicted to result in an exposure that exceeds the nonclinical no-observed-adverse-effect level (NOAEL) exposure in the male rat (i.e., NOAEL exposure at the 50-mg/kg/day dose in male rats in the 28-day GLP toxicity study)
 Parts D, E, and F: 50 mg qd (Part D only), 100 mg qd (Part D only), or 200 mg qd

Active substance: TEZ (tezacaftor; VX-661) and IVA (ivacaftor; VX-770) (Parts C, D, and E)
 Activity: CFTR corrector and potentiator (increased Cl⁻ secretion)
 Strength and route of administration:
 100-mg TEZ/150-mg IVA fixed-dose combination (FDC) (light yellow) film-coated tablet for oral administration
 Dose administered: TEZ 100 mg/IVA 150 mg in the morning

Active substance: IVA (Parts C, D, and E)
 Activity: CFTR potentiator (increased Cl⁻ secretion)
 Strength and route of administration:
 150-mg IVA (light blue) film-coated tablet for oral administration
 Dose administered: 150 mg in the evening

Active substance: VX-561 (deuterated IVA, or CTP-656) (Part F)

Activity: CFTR potentiator

Strength and route of administration:

50-mg VX-561 tablet for oral administration

Dose administered: 150 mg qd

Active substance: TEZ (Part F)

Activity: CFTR corrector (increased Cl⁻ secretion)

Strength and route of administration:

50-mg TEZ (white) tablet for oral administration

Dose administered: 100 mg qd

Study Duration Excluding the Screening Period, the study duration for each subject is as follows:

- Part A, Cohorts A1 through A6: 9 to 12 days
- Part A, Cohort A7: up to 21 to 24 days
- Part B: 18 to 21 days
- Part C: 22 to 25 days
- Parts D1 and D2: approximately 9 weeks (5 weeks for the Treatment Period [consisting of Dosing Periods 1 and 2] and 4 weeks for the Safety Follow-up Period)
- Part E: approximately 16 weeks (4 weeks for the Run-in Period, 4 weeks for the Treatment Period [Period 1], 4 weeks for the Washout Period, and 4 weeks for the Safety Follow-up Period)
- Part F: approximately 8 weeks (4 weeks for the Treatment Period [Period 1] and 4 weeks for the Safety Follow-up Period)

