AE: adverse event; CF: cystic fibrosis; CFQ-R: Cystic Fibrosis Questionnaire-Revised; *CFTR*: CF transmembrane conductance regulator gene; [REDACTED]; ECG: electrocardiogram; ETT: early termination of treatment; FSH: follicle-stimulating hormone; G6PD: glucose-6-phosphate dehydrogenase; ICF: informed consent form; IVA: ivacaftor; PE: physical examination; PK: pharmacokinetic; ppFEV₁: percent predicted forced expiratory volume in 1 second ; TEZ: tezacaftor

^t Blood samples will be collected for PK analysis of VX-445, TEZ, M1-TEZ, IVA, and M1-IVA. On the Day 1 Visit, samples will be collected before dosing (0 hours) and at 1, 2, 4, and 6 hours after dosing (relative to morning dose). On the Day 15 Visit, samples will be collected before dosing (0 hours) and at 1, 2, 4, 6, and 8 hours after dosing. On the Day 29 Visit, a predose sample will be collected before the morning dose of study drug. At the Day 43 Visit, a single blood sample for PK analysis will be collected before the morning dose of TEZ/IVA. At the ETT Visit, a single blood sample for PK analysis will be collected.

^u The last dose of TEZ/IVA will be the morning dose on the Day 57 Visit. See [Section 9.6.2](#) for additional information about study drug administration.

^v The last dose of VX-445 or placebo will be the morning dose on the Day 29 Visit. See [Section 9.6.2](#) for additional information about study drug administration.

^w Refer to [Section 9.5.2](#) for details.

Table 3-8 Study VX16-445-001: Schedule of Assessments for Part F (if Conducted)

Event/Assessment ^a	Screening	Treatment Period: Period 1				ETT Visit ^b	Safety Follow-up 28 (± 7) Days After Last Dose
	Days -28 to -1	Day 1 ^c	Day 8 ^d (± 1 day)	Day 15 (± 2 days)	Day 29 (± 2 days)		
Informed consent	X						
Randomization ^e		X					
Demographics	X						
Medical history	X						
CFQ-R ^{f,g}		X		X	X		
Weight ^h	X	X		X	X	X	X
Height ^h	X						
Vital signs ⁱ	X	X		X	X	X	X
Pulse oximetry ⁱ	X	X		X	X	X	X

^a All assessments will be performed before dosing, unless noted otherwise. Assessments that are collected before and after dosing will only be collected once if study drug is not administered on the day of the visit (i.e., if subject prematurely discontinued study drug treatment).

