9.1.2.4 Treatment Period (Parts D, E, and F)

To be eligible to continue into the Treatment Period, subjects must have stable CF disease and have remained on stable CF medication regimen during the 28 days before the Day 1 Visit AND must not have had an acute non-CF illness within 14 days before the Day 1 Visit.

The VX-445 treatment duration is 4 weeks. The Treatment Period duration is approximately 5 weeks for Parts D1 and D2 (Period 1 + Period 2), 4 weeks for Part E (Period 1), and 4 weeks for Part F (Period 1). All study periods will be conducted as described in [Section 9.1](#). Study drug administration details are provided in [Section 9.6.2](#).

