10 STUDY DRUG INFORMATION AND MANAGEMENT

Study drug refers to VX-445, TEZ/IVA, TEZ, IVA, VX-561, and their matching placebos.

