8.4.1 Adverse Events

For analysis purposes, AEs will be classified as pretreatment AEs, TEAEs, or post-treatment AEs, defined as follows:

For Parts D and F:

Pretreatment AE: any AE that started before the first dose date of study drug

TEAE: any AE that worsened (either in severity or seriousness) or that was newly developed at or after the first dose date of study drug through the end of the TE period

Post-treatment AE: any AE that worsened (either in severity or seriousness) or that was newly developed beyond the TE period

For Part E:

Pretreatment AE: any AE that started before the first dose date of study drug

TEAE during the Run-in Period: any AE that worsened (either in severity or seriousness) or that was newly developed at or after the first dose date of study drug through the end of the TE period for the Run-in Period

TEAE during the Treatment Period: any AE that worsened (either in severity or seriousness) or that was newly developed at or after the first dose date of study drug through the end of the TE period for the Treatment Period

Post-treatment AE: any AE that worsened (either in severity or seriousness) or that was newly developed beyond the TE period

For AEs with completely missing or partially missing start dates, if there is no clear evidence that the AEs started before or after study treatment, the AEs will be classified as TEAEs.

Details for imputing missing or partial start dates of adverse events are described in [Appendix G](#).

AE summary tables will be presented for TEAEs only, for the TE period for Parts D and F, or the TE period for Treatment Period in Part E, by treatment group and overall, for each part respectively, as applicable, for the following:

- Number of TEAEs (total number of TEAEs only)
- Subjects with any TEAEs
- Subjects with TEAEs by Strongest Relationship
- Subjects with TEAEs by Maximum Severity
- Subjects with TEAEs Leading to Study Drug Discontinuation (Discontinuation of all study drug)

- Subjects with TEAEs Leading to Study Drug Interruption (Interruption of all study drug)
- Subjects with Serious TEAEs
- Subjects with TEAE Leading to Death

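### Part E's single treatment-emergent window pools time on VX-445, Washout and follow-up, so the adverse event and threshold tables cannot show which events arose on VX-445

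*SAP*

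**What the plan says.** SAP (Parts D, E and F) section 8.1 sets the start of the Part E window: "The TE period for the Treatment Period will include the first dose of study drug in Period 1 of the Treatment Period". It ends at "28 days after the last dose of study drug or end of study date (based on end of follow-up visit in CRFs), whichever occurs first". Protocol section 10 makes the last dose a TEZ/IVA dose, because "Study drug refers to VX-445, TEZ/IVA, TEZ, IVA, VX-561, and their matching placebos". Protocol Table 3-7 gives the two stopping days: "The last dose of VX-445 or placebo will be the morning dose on the Day 29 Visit" and "The last dose of TEZ/IVA will be the morning dose on the Day 57 Visit". During the Washout Period both randomised groups take TEZ/IVA (SAP Table 6-2, footnote b).

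SAP section 8.4 bases all Part E safety analyses on this window. Section 8.4.1 uses it for every TEAE table, and section 8.4.1's counting rule takes each subject once per event with no adjustment for exposure. Sections 8.4.2 to 8.4.5 use it for the laboratory, ECG and vital-sign threshold tables and for the shift to lowest oxygen saturation.

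Elsewhere the SAP does separate the periods. Disposition is split into Period 1 and Washout (8.2.1), compliance covers Period 1 only (8.2.5), the primary efficacy model uses Period 1 data (8.3.1.1.1), and the Washout has its own model (8.3.1.3.2).

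**The concern.** Safety and tolerability of VX-445 in triple combination is a primary objective of Part E. Period 1 is the only time when the randomised groups take different treatment: "The VX-445 treatment duration is 4 weeks". A table of the percentage of subjects with an event over a much longer window mixes three kinds of event: those arising on VX-445, background events common to both groups, and any that follow the step down from triple combination to TEZ/IVA, which only the TC-high group undergoes. A reader of the planned tables could not tell these apart. A real on-drug excess of a common event could look small, and an excess caused by stopping VX-445 could be read as an on-drug effect.

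**Working it through.** **Length of the window.** Last TEZ/IVA dose on Day 57, plus 28 days, is Day 85. This reproduces the Part E Safety Follow-up target day in SAP Appendix B, Table 11-4. Day 85 − Day 1 = 84 days = 12 weeks, which agrees with the Synopsis (16 weeks in total less the 4-week Run-in). VX-445 occupies 4 of the 12 weeks.

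The 12 weeks is not universal. Early terminators have shorter windows. Subjects who re-enter Study 661-110 after Day 57 have no Safety Follow-up Visit (protocol 9.1.2.6). Depending on the end-of-study date recorded for them, their window may be nearer (57 − 1)/7 = 8 weeks.

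**Effect on the tables.** The documents give no adverse event rates, so the rates below are assumptions. Let p be the control-group risk of at least one event in 4 weeks, with a constant hazard, and let HR be the hazard ratio while on VX-445. Assume no carry-over after Day 29 and no step-down effect. Over k blocks of 4 weeks, of which the first is Period 1:

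- control risk = 1 − (1 − p)^k
- TC-high risk = 1 − (1 − p)^(k − 1 + HR)

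With HR = 1.5 (TC-high v control, difference in points, ratio):

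| p | Period 1 only (4 weeks) | Period 1 + 28-day tail (8 weeks) | Planned window (12 weeks) |
|---|---|---|---|
| 5% | 7.4% v 5.0%; 2.4; 1.48 | 12.0% v 9.8%; 2.3; 1.23 | 16.4% v 14.3%; 2.2; 1.15 |
| 30% | 41.4% v 30.0%; 11.4; 1.38 | 59.0% v 51.0%; 8.0; 1.16 | 71.3% v 65.7%; 5.6; 1.09 |
| 60% | 74.7% v 60.0%; 14.7; 1.25 | 89.9% v 84.0%; 5.9; 1.07 | 96.0% v 93.6%; 2.4; 1.03 |

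Under these assumptions the ratio shrinks in every row. The absolute difference shrinks markedly for common events and hardly at all for rare ones. The 8-week column shows how much of the loss comes from the 28-day tail, which every CF part has. The step from 8 to 12 weeks is what the Washout adds.

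**Step-down.** Take p = 20% and suppose that VX-445 has no on-drug effect but the TC-high hazard doubles during the 4 weeks of Washout. The 12-week risks are 1 − 0.8^4 = 59.0% v 1 − 0.8^3 = 48.8%. A doubling confined to Period 1, with nothing in Washout, gives the same two figures. The pooled table cannot distinguish the two cases.

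**Carry-over.** Take p = 5%, HR = 2 and an effect lasting 2 weeks beyond Day 29. The 12-week difference is (1 − 0.95^4.5) − (1 − 0.95^3) = 20.6% − 14.3% = 6.3 points. Over 4 weeks it is (1 − 0.95^2) − 5% = 4.75 points. Here the longer window shows a larger difference, although the ratio still falls, from 1.95 to 1.45.

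**Precision.** With 18 v 6 subjects, the standard error of a difference is √[p₁(1 − p₁)/18 + p₀(1 − p₀)/6]. In the 30% row this is about 22 points for both the 4-week and the 12-week window. One control subject is 1/6 = 16.7 points.

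**The case against.** The window is not an error. The protocol's own TE definition (12.3.1) gives about the same length, and a 28-day tail after last dose applies in every CF part and catches late events. Measuring the loss against 4 weeks alone therefore treats a standard tail as a defect; the 8-week comparison is fairer. This stands.

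The safety comparison is descriptive, and its imprecision exceeds the dilution. By-visit laboratory, ECG, vital-sign and oximetry summaries are not affected. All adverse events are listed by subject, so a split by onset date could be rebuilt. This also stands, though a rebuild from listings is unplanned work on a primary objective.

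SAP 7.3.2 says that the Part E Safety Set implicitly means the one for Period 1. That note defines which subjects are counted, not the time over which their events are counted, so it does not answer the point.

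A reader might also infer that 8.4.1 starts Treatment Period TEAEs at Day −28, because its definition ("TEAE during the Treatment Period: any AE that worsened" and onward) does not say which first dose it means. The documents do not support that reading. Section 8.1 fixes the start at the first Period 1 dose, sections 8.4 and 8.4.1 tie the analyses and tables to that window, and Appendix G classifies events by comparing their start date with it. The missing qualifier is editorial.

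**Conclusion.** The point holds in a limited form, as something to consider. For subjects who complete follow-up, the Part E TEAE and threshold tables cover 12 weeks, of which 4 are on VX-445 or placebo, and no planned table separates on-drug events from background or step-down events.

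A reader might infer that the plan biases the comparison towards no difference. The documents do not establish that. It would require the VX-445 effect to end soon after Day 29 and no effect of stopping, whereas only TC-high loses a drug at that point, and the Washout was designed to observe that step down for PD and efficacy endpoints. The direction is therefore not known.

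If both conditions hold, the ratio is diluted at every background rate tried. At an assumed HR of 1.5, the loss in absolute difference ranges from 0.2 points (2.4 to 2.2, at 5% background per 4 weeks) to 5.8 points at 30% (11.4 to 5.6, or 8.0 to 5.6 against Period 1 plus the tail) and 12.3 points at 60% (14.7 to 2.4). All these rates are assumptions.

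**What to change.** Keep the overall TE tables, so that late events are not lost. Add Part E summaries of TEAEs, serious TEAEs and threshold events by onset in three periods: Period 1 (Day 1 to Day 29), Washout, and follow-up. Give the number of subjects still under observation in each period, because windows differ between subjects.

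As an editorial correction, add to the Treatment Period TEAE definition in SAP 8.4.1 the qualifier that section 8.1 already carries, naming Period 1 of the Treatment Period as the source of the first dose.

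The cost is a few extra descriptive tables, which will be sparse with 6 control subjects, and one amended sentence. No new data are needed and the design does not change.
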